#### 7.8.1 Investigator Symptom Score

The primary efficacy endpoint is the time to onset of symptom relief measured using the investigator-reported symptom score. Eight symptoms will be assessed for abdominal and cutaneous attacks, and 13 symptoms will be assessed for laryngeal attacks. Time to onset of symptom relief is defined as the duration of time in hours from study drug administration to the earliest time post-treatment at which there is at least a 20% improvement in the composite (or average) post-treatment symptom score with no worsening of any single component score.

Subjects not achieving the onset of symptom relief will be censored at the time of their last symptom assessment. Time to onset of symptom relief will be summarized using the Kaplan-Meier method.

An alternative efficacy endpoint is the time to minimum symptoms measured using the investigator-reported symptom score. It is defined as the earliest time post-treatment when all symptoms are either mild or absent. Subjects not achieving the minimum symptom criteria will be censored at the time of their last symptom assessment. Time to minimum symptoms will be summarized using the Kaplan-Meier method. Subjects with all symptoms as mild or absent at pretreatment will be excluded from this analysis.

The composite investigator-reported symptom score and the change from pre-treatment in the composite investigator-reported symptom score will be summarized by study time-point. Furthermore, the symptom scores associated with individual symptoms will be summarized by study time-point. The mean composite investigator-assessed symptom score will be plotted by study time-point by pubertal status stratification group.

For individual investigator-reported symptom scores, a shift table from baseline will be presented for each post-treatment time point. The analysis will be repeated to assess shift in the individual symptom scores from the 2 hour time-point.

Time to onset of symptom relief for individual symptom is defined as duration of time in hours from study drug administration to the earliest time post-treatment when the specific symptom is either mild or absent. Subjects not achieving the relief for individual symptom criteria will be censored at the time of their last symptom assessment. Time to onset of symptom relief for individual symptoms will be summarized using the Kaplan-Meier method. Subjects with the individual symptom as mild or absent at pretreatment will be excluded from the analysis on that symptom.

Analyses on investigator symptom score will be performed for the initial icatibant exposure and both subsequent exposures.

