6.7 Rescue Therapy

For the purposes of this protocol, rescue therapy is any medication used after the administration of icatibant which, in the opinion of the investigator, is immediately necessary to alleviate acute symptoms which are judged by the investigator as resultant from the current HAE attack. For subjects treated at home for a subsequent attack, subjects must contact the hospital/study center (or their home healthcare professional in the event the investigator is not available) if symptom

improvement is not seen after the administration of icatibant and they believe they need additional treatment to alleviate acute symptoms.

Repeat administration of icatibant for treatment of a single attack is not allowed in this study.

The determination of the necessity for rescue therapy will be at the discretion of the investigator. With the exception of icatibant, any medicinal product may be used as rescue medication at the discretion of the treating physician.

Rescue therapies will include agents to control the HAE attack, such as C1-INH inhibitor concentrates. C1-INH therapy has been used safely for the treatment of acute attacks in the pediatric setting (Farkas 2010). If C1-INH concentrates are unavailable, FFP may be used (Zuraw 2008). A kallikrein inhibitor, ecallantide, approved only in the United States of America (USA), is indicated for use in patients 16 years of age and older.

Other acceptable rescue therapies for acute attacks include palliative medications that are intended to ameliorate the symptoms (eg, pain, nausea) of angioedema rather than to control the HAE attack itself. If pain medication is required, the investigator may administer IV or prescription-strength non-steroidal anti-inflammatory drugs (NSAIDs) for mild to moderate pain and administer morphine sulfate (or opiate equivalent) intravenously or intramuscularly at a dose of 0.05 mg/kg (or an equivalent dose if another opiate medication is used). Anti-emetics may also be prescribed as necessary to treat nausea. Acceptable rescue therapies may also include epinephrine, IV fluids, or other medicinal products.

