### 7.8.4 Other Efficacy Analyses

#### Time to First Use of Rescue Medication

The number and percentage of subjects who received rescue medications before the onset of symptom relief will be summarized. Time to first use of rescue medication prior to onset of symptom relief will be calculated from the time of study drug administration to the first use of rescue medication prior to the onset of symptom relief. Subjects not using rescue medication prior to the onset of symptom relief will be censored at the time of their onset of symptom relief. Time to first use of rescue medication will be summarized using the Kaplan-Meier method. This analysis will only be performed if there are at least 5 subjects for a given attack who used rescue medication prior to attaining symptom relief.

Subjects who received rescue medication before the onset of symptom relief will be denoted in the listing on rescue medication for the efficacy population.

Analyses on time to first use of rescue medication will be performed for the initial icatibant exposure and both subsequent icatibant exposures.

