#### **9.7 Sensitivity Analyses**

No sensitivity analysis is planned for this study.

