### 10.2.4 Time-to-Event Endpoints

Time-to-event endpoints will be calculated from the time of study drug administration to the earliest time point at which endpoint is achieved. The actual study drug administration date and time, and the first assessment date and time at which at the endpoint criteria is satisfied will be used for this calculation.

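### Relief reached after rescue medication counts as an event in both time-to-relief endpoints, and no planned analysis shows relief achieved without rescue

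*SAP*

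**What the plan says.** SAP 7.8.1 names the endpoint: "The primary efficacy endpoint is the time to onset of symptom relief measured using the investigator-reported symptom score". In the study's own hierarchy (SAP 5, protocol 3) the primary endpoints are PK and safety, and time to relief is secondary. The event is the first assessment showing "at least a 20% improvement in the composite (or average) post-treatment symptom score with no worsening of any single component score". On censoring, the section says: "Subjects not achieving the onset of symptom relief will be censored at the time of their last symptom assessment". Time to minimum symptoms, when all symptoms are mild or absent, has the same form.

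The programming rule in SAP 10.2.4 adds no condition: "Time-to-event endpoints will be calculated from the time of study drug administration to the earliest time point at which endpoint is achieved". Protocol 10.7 has no rule for rescue either.

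Protocol 6.7 leaves the choice of rescue wide open: "With the exception of icatibant, any medicinal product may be used as rescue medication at the discretion of the treating physician". It also says: "Rescue therapies will include agents to control the HAE attack, such as C1-INH inhibitor concentrates". Pain medication and anti-emetics are acceptable as well.

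SAP 7.8.4 does address rescue: "The number and percentage of subjects who received rescue medications before the onset of symptom relief will be summarized". Those subjects are flagged in a listing, and time to first rescue is analysed by Kaplan-Meier if at least 5 subjects for a given attack used rescue before relief. SAP 9.7 states: "No sensitivity analysis is planned for this study".

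**The concern.** A subject who takes an effective rescue agent and then improves is recorded as relieved at the next qualifying assessment, exactly like a subject who improved on icatibant alone. The study has one arm, so no comparator carries the same contamination. SAP 4.2 nevertheless says the study is meant to demonstrate effectiveness, and protocol 1.2.2 attributes rapid resolution to icatibant.

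The endpoint is also easily moved by palliative treatment. Nausea, vomiting, skin pain and abdominal tenderness are among the 8 scored symptoms, and mild attacks are eligible. If the pretreatment total is 5 or less, a one-point fall in one symptom is at least 1/5 = 20%. That meets the criterion if nothing else worsens.

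At stake is how the Kaplan-Meier results are read: whether the reported times describe relief after icatibant, or relief after icatibant plus whatever else was given.

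**Working it through.** **1. Can post-rescue relief be an event?** SAP 7.8.1 and 10.2.4 set no rescue condition, and only subjects without relief are censored. SAP 7.8.4 analyses rescue taken before relief, so the plan foresees the sequence rescue, then relief, and leaves the relief endpoint unchanged. Post-rescue relief therefore counts by silence, not by an explicit rule.

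**2. Direction.** Compare the planned rule with an alternative in which rescue before relief means no relief and the subject stays at risk to a common time at or after the last assessment. At every event time the alternative has no more events and no fewer subjects at risk. Its Kaplan-Meier curve is therefore never below the planned one, and its times are equal or longer.

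**3. Size per subject.** The plan expects at least 20 subjects treated in an attack, 10 per pubertal group (SAP 4.1). One subject relieved after rescue adds 1/10 = 10 points to the proportion relieved in a group of 10, and 1/20 = 5 points overall. Example for a group of 10: 6 are relieved by 1 h, 2 of them after rescue. The planned median is 1 h. Without those two, 4/10 = 40% are relieved at 1 h, and the median moves to 2 h or later.

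**4. Illustration on assumed data.** The documents give no subject data and no rescue rate. Assume N = 20, with relief at 1 h in 12, 2 h in 4, 4 h in 3 and 6 h in 1. The planned rule gives 20 events, median 1 h and 75th percentile 2 h, however many were rescued. Under the alternative (censored at 8 h), with k subjects rescued before relief, and with percentiles read as the first time the curve is at or below the level:

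| k | Events | Unrelieved (k/20) | Latest relievers rescued: median / 75th | Rescued before the 1 h score: median / 75th |
|---|---|---|---|---|
| 1 | 19 | 5% | 1 h / 2 h | 1 h / 2 h |
| 2 | 18 | 10% | 1 h / 2 h | 1 h / 4 h |
| 3 | 17 | 15% | 1 h / 2 h | 2 h / 4 h |
| 4 | 16 | 20% | 1 h / 2 h | 2 h / 4 h |
| 5 | 15 | 25% | 1 h / 2 h | 2 h / 6 h |
| 6 | 14 | 30% | 1 h / not reached | 2 h / not reached |

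The proportion relieved always falls. The median moves only with early rescue.

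**5. The reported median.** Protocol 1.2.2 gives an overall initial median of 1.0 h (95% CI 1.0, 1.1). It cannot be rebuilt without subject data, but it can be bounded. Assume N = 20 to 25 (not stated), little censoring, and the usual limit: the first time at which (0.5 − S)/√(S(1 − S)/N) exceeds 1.96.
- N = 20: S = 6/20 gives 0.20/0.1025 = 1.95, not enough; S = 5/20 gives 0.25/0.0968 = 2.58. So at least 15 were relieved by 1.1 h.
- N = 25: S = 8/25 gives 0.18/0.0933 = 1.93, not enough; S = 7/25 gives 0.22/0.0898 = 2.45. So at least 18 were relieved by 1.1 h.

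Log-log limits give the same counts. To move the median, those relieved by 1.1 h must fall to 9 of 20 (10 if a tie at 50% is averaged) or 12 of 25. That removes 15 − 9 = 6 (or 15 − 10 = 5), or 18 − 12 = 6, all rescued and relieved within about 1.1 h.

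**6. What SAP 7.8.4 would show.** The count and listing always appear. The time-to-rescue analysis needs 5 subjects per attack, so 4 of 20 (20%) or 4 of 10 (40%) would not trigger it. For an assumed rescue rate of 5%, 10%, 20% or 30%, the binomial chance of reaching 5 is 0.003, 0.043, 0.370 or 0.762 for N = 20. For N = 10 it is below 0.001, 0.002, 0.033 or 0.150.

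**The case against.** The planned rule is a recognised treatment-policy choice in a descriptive study with no hypothesis test and no formal sample size. Rescue is not hidden. SAP 7.8.4 counts and flags subjects rescued before relief, rescue incidence is a secondary endpoint, and SAP 7.1 lists each subject's contribution to every time-to-event analysis. With about 20 subjects, a reader could rebuild the adjusted result by hand. All of that stands, and it is why the main analysis need not change.

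It does not close the gap. The 7.8.4 count mixes subjects rescued and later relieved with subjects rescued and never relieved, and a listing is not a prespecified estimate.

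Three stronger readings are tempting, and the documents do not support them:
- A reader might infer that the effect of rescue is invisible. SAP 7.8.4 and 7.1 show otherwise. Moving the overall initial median would take 5 or 6 very early rescues (on the assumed N), enough to trigger the time-to-rescue analysis as well.
- A reader might infer that the rule always overstates icatibant's effect. Step 2 shows only that it is never slower than rescue-as-failure. A child already improving who is given an anti-emetic might have been relieved anyway, and rescue-as-failure would then understate the effect.
- A reader might take the 5-subject threshold as a plausible rescue rate, giving 5/20 = 25 points. It is a trigger for an analysis, and it also counts subjects never relieved, who add nothing to the proportion relieved.

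**Conclusion.** The point holds in limited form. Relief after rescue is an event in both endpoints, the plan does not say so, and nothing planned estimates relief without rescue. Against rescue-as-failure the direction is certain. The size is unknown because the documents give no rescue rate.

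The reported overall initial median is robust unless several subjects were rescued within about the first hour; that bound assumes N of 20 to 25 and little censoring. More exposed are the upper quartiles (SAP 7.1 requires the 75th percentile), the proportion relieved, the pubertal groups of about 10, and exposures 2 and 3. Those later exposures are split by administration type, and the investigator score is recorded only for subjects treated at the site. FPS-R and FLACC times share the gap. This is a cheap improvement, not a flaw that invalidates the analysis.

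**What to change.** Keep the main analysis. In SAP 7.8.1, state that it counts relief regardless of rescue.

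In SAP 9.7, replace the statement that nothing is planned with one supplementary analysis of time to onset of symptom relief and time to minimum symptoms, by exposure number. A subject with rescue medication, as defined in SAP 10.2.14, before the event is counted as not achieving it. Keep such subjects at risk and censor them at a stated common time at or after the last assessment for that exposure. Examples are 8 h for the initial attack (or the latest actual assessment, if one falls later within the visit window), and the latest assessment time observed in the exposure group for subsequent attacks. Do not censor at rescue or at the subject's own last score. Initial scoring ends at 6 or 8 h (protocol 8.3.2), and later attacks are scored only until symptoms are mild or absent (protocol 8.4.2.1), so a subject's own last score depends on outcome. Show the number relieved without prior rescue beside the main result.

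Cost: about four small tables (two endpoints, for exposure 1 and for exposures 2 and 3) and one new derivation, rescue before minimum symptoms; SAP 7.8.4 already derives rescue before relief. The reported time may look slightly longer, and the analysis may be conservative where rescue was only palliative. No data collection or clinical rule changes.

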4.1.2 Study Methodology

A subject's classification as prepubertal or pubertal/postpubertal will be determined at screening and, if classified as prepubertal at screening will have their pubertal status reassessed at the time of their first icatibant-treated attack visit.

Initially, enrollment and dosing of pubertal/postpubertal subjects will precede that of prepubertal subjects. After the first 4 subjects in the pubertal/postpubertal group have been treated with icatibant (whether during or in the absence of attack), PK, safety/tolerability, and efficacy (as appropriate) will be reviewed by an independent Data and Safety Monitoring Board (DSMB). The DSMB review of the first 4 subjects shall be completed prior to continuing enrollment of additional pubertal/postpubertal subjects, treatment of second and third HAE attacks in pubertal/postpubertal subjects, and initiating enrollment of subjects in the prepubertal group.

Initial Icatibant Treatment

After a qualifying screening period, the PK, safety/tolerability, and efficacy of treatment with SC icatibant will be evaluated in at least 20 subjects (10 prepubertal and 10 pubertal/postpubertal subjects) who present with cutaneous, abdominal, or laryngeal symptoms of an acute attack of HAE. Subjects should initiate treatment with icatibant within 12 hours of the onset of symptoms; however, there are no prespecified attack severity criteria that are required for treatment. Subjects with attacks considered to be mild, moderate, or severe are all potentially eligible to receive treatment with icatibant.

The PK and safety/tolerability of SC icatibant will be evaluated in at least 10 additional pubertal/postpubertal subjects who meet screening criteria, but receive treatment with SC icatibant in the absence of a current acute HAE attack.

Subjects will receive treatment with a single SC administration of icatibant on Day 1 and will be monitored closely in the hospital/study center for at least 6 to 8 hours after treatment. Subjects will undergo PK and safety assessments; efficacy assessments will be performed if treatment occurs during an acute HAE attack. All subjects will have serum reproductive hormone measurements.

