*A subject may be discharged after completion of all assessments at 6 hours post treatment, if deemed medically stable in the investigator's clinical judgment and the subject's HAE symptoms have resolved (the subject's investigator-rated symptom score = zero, denoting the absence of symptoms).

If this is the case, the assessments scheduled for 8 hours post treatment will be omitted with the exception of subject self-assessment of HAE-related pain using the diary FPS-R.

**If the subject's HAE symptoms have not resolved at 6 hours post treatment (the subject's investigator-rated symptom score \neq zero) and the subject is not to be discharged after completion of assessments at the 6-hour time point, the assessments indicated will be performed at both 6 AND 8 hours post treatment.

***If the subject's HAE symptoms have not resolved at 6 hours post treatment (the subject's investigator-rated symptom score \neq zero) and the subject is not to be discharged after completion of assessments at the 6-hour time point, the assessments indicated will be performed at either 6 OR 8 hours post treatment.

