10.2 Determination of Sample Size

The study will enroll a sufficient number of children and adolescents to ensure study completion of 30 subjects. The study population is planned to consist of at least 10 prepubertal and 20 pubertal/postpubertal subjects from 2 to less than 18 years of age. Though empirically derived and not based on a formal sample size calculation, this sample size will provide basic information concerning the PK, tolerability and safety, and efficacy of icatibant in children and adolescents with HAE.

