10.10 Handling of Missing Data

Individual pretreatment symptom scores, FPS-R scores, and FLACC scores will be assigned a value of zero. For missing post-treatment scores, imputation will be employed using the Last Observation Carried Forward (LOCF) approach. The pretreatment values may also be used in the imputation. For missing or partial rescue medication dates, the imputation will be performed such that the earliest possible time post treatment will be assigned to the rescue medication use. A similar approach will be followed to determine treatment emergent AEs in case of missing or partial AE dates.

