^a All evaluations and sample collections must be performed at the hospital/study center within 6 months prior to treatment if a repeat attack does not occur within 6 months. If a second “baseline” visit is conducted due to lack of repeat attacks, one of the monthly phone calls may overlap with the onsite visit. In this case, a monthly call would not be necessary.

^b These assessments may be conducted by telephone contact.

^c If a subsequent attack occurs within 3 days of the Day 8 follow-up visit for the previous attack, the visits for Day 1 (of the subsequent icatibant-treated attack) and Day 8 (of the prior icatibant-treated attack) will be combined. If a subsequent attack occurs within 7 days of the Day 90 follow-up visit for the previous attack, the visits for Day 8 (of the subsequent icatibant-treated attack) and Day 90 (of the prior icatibant-treated attack) will be combined.

^d For subjects who have expressed an interest in self-administering or having a parent/legal guardian/caregiver administer icatibant in the home.

^e For subsequent attacks, study drug may be administered by study site personnel at the hospital/study center or by qualified home healthcare personnel at the subject’s home. Alternatively, a parent/legal guardian/caregiver will be allowed to administer or the subject (under the supervision of a parent/legal guardian/caregiver) will be allowed to self-administer the investigational product after having received appropriate training. For all subsequent laryngeal attacks, subjects should be advised to seek medical attention in an appropriate healthcare facility immediately following treatment with icatibant.

^f If after the completion of the assessments scheduled for 2 hours post-treatment, the subject’s pain is absent, no further Day 1 assessments are required. If the subject’s pain at 2 hours post-treatment is NOT absent, the subject will be assessed every 2 hours until pain is absent.

^g For subjects treated at the hospital/study center only.

^h The subject will be observed for a minimum of 2 hours after icatibant administration. If after the completion of the assessments scheduled for 2 hours post-treatment, the subject’s symptoms are absent or mild, no further Day 1 assessments are required. If the subject’s symptoms at 2 hours post-treatment are moderate, severe, or very severe, the subject will be assessed every 2 hours until the subject’s symptoms are absent or mild.

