### 7.9.2 Symptoms at Injection Site

Injection site reactions (erythema, swelling, burning sensation, itching/pruritus, warm sensation, cutaneous pain) will be evaluated by the investigator or home healthcare provider/parent/legal guardian/caregiver when the subject is at the hospital/study center.

The number and percentage of subjects with any injection site reactions, and any severe reactions, will be summarized by type of reaction.

The number and percentage of subjects with injection site reactions will be summarized by maximum severity at any time point and for each study time point.

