### **9.2 Handling of Dropouts or Missing Data**

#### **9.2.1 Handling of Missing Data in Efficacy Assessments**

In general, a conservative approach that is unlikely to bias the results will be used to deal with missing data. Individual missing pretreatment scores, when the assessment was performed (i.e., other instrument-specific pretreatment scores are non-missing), will be assigned a value of mean value from the other available symptom scores when calculating the composite symptom scores at baseline.

Individual missing post-treatment scores, when the assessment was performed (i.e., other instrument-specific scores are non-missing), will be assigned the last non-missing value using last observation carried forward (LOCF). If the baseline observation is the last non-missing value it will be carried forward as well. This imputation method assumes that if an investigator did not rate a symptom at a particular assessment, then there was no change from the previous assessment.

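### Late by-time-point symptom means rest on subjects selected for slower response, because scoring stops on improvement and the SAP has no rule for assessments omitted by design

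*SAP*

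**What the plan says.** **Outputs.** SAP 7.8.1: "The composite investigator-reported symptom score and the change from pre-treatment in the composite investigator-reported symptom score will be summarized by study time-point". The mean composite is also plotted by time point, by pubertal group. The outputs are Tables 14.2.3.1-2 and Figures 14.2.3.1-2. SAP 7.8.3 summarises FLACC by time point as well.

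**Initial attack.** All subjects are scored at 1, 2, 4 and 6 h. Protocol 10.7 limits the 8 h score to subjects without complete resolution at 6 h. The discharge footnote in Protocol 8.3.2 says of subjects sent home at 6 h with a score of zero: "If this is the case, the assessments scheduled for 8 hours post treatment will be omitted with the exception of subject self-assessment". That exception is the FPS-R diary, so FPS-R continues for everyone aged 4 or older. The investigator score and FLACC do not.

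**Repeat attacks.** Protocol 8.4.2.1 and Appendix 3 score at 1 and 2 h, then every 2 h while symptoms are moderate or worse. If at 2 h "symptoms are absent or mild, no further Day 1 assessments are required". Protocol 10.7 differs: it has the investigator continue every 2 h up to discharge. Injection site reactions follow a similar Day 1 stop (mild or absent), but are recorded again on Day 2 and Day 8 without a severity condition. SAP 7.9.2 says that they "will be summarized by maximum severity at any time point and for each study time point".

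**Missing scores.** Protocol 10.10: "For missing post-treatment scores, imputation will be employed using the Last Observation Carried Forward (LOCF) approach". SAP 9.2.1: "Individual missing post-treatment scores, when the assessment was performed (i.e., other instrument-specific scores are non-missing), will be assigned the last non-missing value". SAP 8.2 reports no change from the protocol's analyses, and SAP 9.7 plans no sensitivity analysis.

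**The concern.** Whether a subject has a late score depends on how well that subject has done. Subjects who improve leave the denominator, and the SAP's carry-forward rule does not bring them back because no assessment took place. The late means then describe slower responders, while the 1 to 6 h means (1 and 2 h in repeat attacks) describe everyone scored. Joined on one curve, the two can suggest that symptoms return or the effect fades when no subject has worsened.

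In a single-arm study the mean curve is a direct display of response. Worsening between 2 and 4 h is also a listed secondary endpoint, so readers will look at the later points for signs of return.

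**Working it through.** **Inputs.** There is no design figure to reproduce; of the sample size Protocol 10.2 says "Though empirically derived and not based on a formal sample size calculation". Protocol 4.1.2 gives the number scored at the initial attack: efficacy "will be evaluated in at least 20 subjects (10 prepubertal and 10 pubertal/postpubertal subjects"). All response quantities below are assumptions, shown over a range, because the documents do not give them.

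**Initial attack.** Let p be the share with a score above 0 at 6 h, m6 their mean score at 6 h, and r their 8 h mean divided by their 6 h mean.

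- Plotted 6 h mean, all subjects: p × m6
- Plotted 8 h mean, unresolved subjects only: r × m6
- 8 h mean with resolved subjects kept at 0: p × r × m6
- Overstatement at 8 h: (r × m6)/(p × r × m6) = 1/p
- Plotted 8 h/6 h ratio: r/p, so the curve rises only if r > p. With zeros kept, the ratio is r.

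Plotted 8 h/6 h ratio (above 1 is a rise):

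| p | r = 0.25 | r = 0.5 | r = 0.75 | r = 1.0 | 1/p |
|---|---|---|---|---|---|
| 0.1 | 2.5 | 5.0 | 7.5 | 10.0 | 10 |
| 0.2 | 1.25 | 2.5 | 3.75 | 5.0 | 5 |
| 0.3 | 0.83 | 1.67 | 2.5 | 3.33 | 3.33 |
| 0.5 | 0.5 | 1.0 | 1.5 | 2.0 | 2 |
| 0.8 | 0.31 | 0.625 | 0.94 | 1.25 | 1.25 |

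Two examples with 20 subjects, where each unresolved subject has one mild symptom of eight (1/8 = 0.125):

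- *6 unresolved at 6 h, 2 of them clear by 8 h.* 6 h mean 6 × 0.125/20 = 0.0375. Plotted 8 h mean 4 × 0.125/6 = 0.0833, a rise. With zeros kept, 4 × 0.125/20 = 0.0250, a fall.
- *12 unresolved at 6 h, 8 of them clear by 8 h.* 6 h mean 12 × 0.125/20 = 0.0750. Plotted 8 h mean 4 × 0.125/12 = 0.0417, a fall. With zeros kept, 0.0250.

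No subject worsens in either example. The plotted 8 h mean is too high in both, but it rises only in the first.

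**Repeat attacks, under the absent-or-mild stop.** Let q be the share moderate or worse at 2 h, M their 2 h mean, L the 2 h mean of those who stop, and r the 4 h/2 h ratio in those who continue.

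- 2 h mean, all scored: qM + (1 − q)L
- Observed 4 h mean: rM
- 4 h mean with stopped subjects carried forward: q·rM + (1 − q)L
- Overstatement: (1 − q)(rM − L), which is upward when rM > L
- A rise needs r > q + (1 − q)L/M

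Assume M = 0.75, L = 0.125, r = 0.5:

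- *q = 0.3.* 2 h mean 0.3 × 0.75 + 0.7 × 0.125 = 0.3125; observed 4 h mean 0.375 (rise); carried forward 0.3 × 0.375 + 0.7 × 0.125 = 0.200 (fall).
- *q = 0.5.* 2 h mean 0.4375; observed 0.375 (fall); carried forward 0.250.

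The stopping criterion matches the plan's definition of minimal symptoms. Protocol 1.2.2 reports a median time to minimal symptoms of 1.1 h (95% CI 1.0, 2.0) at the initial attack. If repeat attacks respond similarly, q would be below 0.5.

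**The case against.** **For leaving it alone.** The efficacy endpoints are Kaplan-Meier times, and no hypothesis test uses these means. Under SAP 7.1 every continuous summary reports the number of subjects, and results are listed by subject. Observed-case description with n is conventional, and carrying scores forward makes its own assumption. Initial-attack FPS-R continues at 8, 24 and 48 h for subjects aged 4 or older, which gives an unselected check on pain. FLACC covers only those under 4 and has no mean plot. The differences in the examples are small on a 0 to 4 scale.

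This limits the consequence but leaves the bias in place. A falling n shows that subjects have left, not that they left because they were well, and the figure description does not mention n. With about 10 subjects per pubertal group, p between 0.1 and 0.3 leaves one to three children behind an 8 h point. Tabulating change from pre-treatment does not help, because it uses the same subset.

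**On the wording.** Protocol 10.10 does not say whether its carry-forward covers assessments that the schedule omits, so it is a reasonable reading, not a certainty, that the SAP narrows it. Appendix 3 has no 4 h column, and Protocol 10.7 conflicts with the stopping rule, so the repeat-attack time points to be tabulated are not settled. Both points stand, and both are reasons to write the rule down.

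**Stronger readings that the documents do not support.** A reader might infer that the plotted score must rise at 8 h. It need not: the second example falls. Nor are the subjects scored at 8 h necessarily still symptomatic; they were unresolved at 6 h and may score 0 by 8 h. A reader might also infer that late injection site percentages in repeat exposures approach 100%. SAP 7.9.2 sets no denominator; with the Safety Population as denominator this would not happen. Day 2, Day 8 and maximum severity are not subject to the selection.

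**Conclusion.** The point holds as a bias in descriptive outputs. As the SAP is written, the 8 h composite mean at the initial attack is too high by a factor 1/p, provided that resolved subjects stay at 0. A resolved subject kept in for another reason would be the one exception to the selection. FLACC at 8 h has the same selection.

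Under the schedule's stopping rule, Day 1 means after 2 h in repeat attacks are also selected. They are biased upward whenever continuing subjects average above those who stopped. A spurious rise is possible at 8 h when r > p, and likely when few subjects are unresolved at 6 h. Neither p nor r is in the documents, so the size can only be given as a range.

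The Kaplan-Meier endpoints and initial-attack FPS-R are unaffected. Day 1 injection site percentages after 2 h in repeat exposures are affected only if the denominator is those still assessed.

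**What to change.** In SAP 9.2.1, for by-time-point summaries and plots only:

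- Set the 8 h composite to 0 for subjects discharged at 6 h with a score of 0. For FLACC, carry the 6 h total forward, since the symptom score triggers the stop.
- In repeat attacks, carry the last score through the remaining Day 1 time points once the stopping rule is met.
- Alternatively, end the mean plots at 6 h for exposure 1 and at 2 h for exposures 2 and 3.

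In either case:

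- Show n observed and n carried under each table and figure.
- State the denominator for Day 1 injection site percentages in SAP 7.9.2.
- Reconcile Protocol 10.7 (scoring up to discharge) with Protocol 8.4.2.1 and Appendix 3 (stop when absent or mild), and say which repeat-attack time points will be tabulated.
- List the carry-forward change in SAP 8.2.
- Leave the time-to-event analyses as they are.

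The cost is SAP wording and a small derivation, with no new data. The downside is that carried values assume no return of symptoms after scoring stops; the count of carried values shows how far each mean depends on that. Truncating the plots avoids the assumption but gives up the late points.
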